11.2.5.4 Analysis of Unsolicited Adverse Events

If the reporting source is collected in the study, specify the following: The first-line analysis will use unsolicited AE data from all reporting sources combined. A second-line analysis will encompass the analysis of unsolicited AEs by source (medical records, study specific worksheet).

All the unsolicited AEs occurring during the study, judged either as probably related, possibly related, or not related to vaccination by the investigator, will be recorded through the day 22 clinic visit. AEs leading to withdrawal, AESI, NOCD and SAEs up to Day 181 will be captured. The original verbatim terms used by investigators to identify AEs in the CRFs will be mapped to lowest level term using the MedDRA dictionary. The unsolicited AEs will then be grouped by MedDRA preferred terms into frequency tables according to primary system organ class. AEs judged by the investigator as at least possibly related to study vaccine will be summarized by vaccine group, according to system organ class and preferred term within system organ class. When an unsolicited AE occurs more than once for a subject, the maximal severity and strongest relationship to the vaccine group will be counted.

Only vaccine-emergent AEs (see Section 8.7 for definition) will be analyzed, i.e., excluding those after a subject has given informed consent but before vaccination. The selection of unsolicited AEs and the assignment to time intervals will be done by day of onset and not by days ongoing/persisting.

The summaries will be presented by period of onset and will include frequency distributions of the different AEs:

- Onset between Day 1 and Day 22.
- Onset between Day 23 and Day 181.
- Onset between Day 1 and Day 181

The analysis of unsolicited AEs comprises the following categories:

- Any unsolicited AE.
- Possibly or probably related unsolicited AEs.
- Unsolicited AEs leading to death.
- Serious adverse events (SAEs).
- Possibly or probably related SAEs.
- Unsolicited AEs leading to premature withdrawal from study.
- Unsolicited AEs leading to NOCD.
- Unsolicited AEs of special interest.

Solicited AEs continuing beyond Day 7 will be coded by MedDRA and will also be reported as unsolicited AEs.

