A reminder telephone call will be made on Day 3 (window, Day 2 to Day 4) to remind the subject to complete the Diary Card.

A scripted safety telephone call will be made by qualified site staff on Day 15 (window: Day 12 to day 18) to collect any unsolicited AEs and any use of concomitant medications: these will be captured in the electronic Case Report Form (CRF).

Subjects will return to the clinic on Day 22 (window, Day 19 to Day 25) for a medical examination, and to provide a blood sample for serologic testing. During this visit Diary Cards will be collected and all unsolicited AEs and concomitant medication use (occurring after vaccination between Day 1 and Day 22) will be documented in the subject's source records and captured in the CRF.

Any subject who manifests signs of an influenza-like illness (ILI, defined as at least one of the following respiratory symptoms: sore throat, cough, sputum production, wheezing, or difficulty breathing; concurrently with at least one of the following systemic symptoms: temperature of  $>37.2^{\circ}\text{C} / 99^{\circ}\text{F}$ , chills, tiredness, headache, or myalgia) during the may be performed at any time during the Treatment Period(Days 1-22) will be evaluated by real time reverse transcription polymerase chain reaction (RT-PCR) testing of a nasopharyngeal (NP) specimen for influenza. Swabs will be sent to a qualified central laboratory as specified in the Clinical Investigator Laboratory Manual. Subjects with onset of ILI and RT-PCR-confirmed influenza during the Treatment Period (Days 1-22) will be removed from the Per Protocol Set (PPS) in the immunogenicity analyses. ILI will also be recorded as an adverse event.

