### **Follow-up Period: Day 23 through Day 181**

A scripted safety telephone call will be made by qualified site staff on Day 91 (window: Day 84 to Day 98) to collect only those unsolicited AEs that are: serious AEs (SAEs), AEs leading to study withdrawal, new onset of chronic diseases (NOCDs), adverse events of special interest (AESIs); and concomitant medications associated with these events.

A scripted safety telephone call will be made by qualified site staff on Day 181 (window: Day 167 to Day 195) for assessment of SAEs, AEs leading to study withdrawal, NOCDs, and AESIs; and concomitant medications associated with these events.

An unscheduled study visit may be performed as necessary for further evaluation of safety information that is described on the telephone that is to be investigated further at any time during the study.

A clinical study report will present immunogenicity and safety data collected through the final evaluation (6 months following vaccination, Day 181).

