### **7.1.2 Unsolicited Adverse Events**

An unsolicited adverse event is an adverse event that was not solicited using a Diary Card and that was spontaneously communicated by a subject or legal representative(s) who has signed the informed consent.

All unsolicited adverse events, and medications used to treat them, will be collected from study admission (at the time of informed consent) through the Day 22 clinic visit. After the day 22 visit, only unsolicited adverse events, and medication used to treat them, which meet criteria for the following will be collected: serious adverse events, adverse events of special interest, new onset of chronic disease, and events leading to study discontinuation.

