#### **8.4.4.3 Analysis of Unsolicited Adverse Events**

This analysis applies to all adverse events occurring during the study, judged either as probably related, possibly related, or not related to vaccination by the Investigator, recorded in AE CRF, with a start date on or after the date of first vaccination. AE starting prior to the first vaccination will only be listed. The original verbatim terms used by investigators to identify adverse events in the CRFs will be mapped to preferred terms using the MedDRA dictionary. The adverse events will then be grouped by MedDRA preferred terms into frequency tables according to system organ class.

All reported adverse events, as well as adverse events judged by the investigator as at least possibly related to study vaccine, will be summarized according to system organ class and preferred term within system organ class (SOC). These summaries will be presented by vaccination group and by interval of study observation. When an adverse event occurs more than once for a subject, the maximal severity and strongest relationship to the vaccine group will be counted.

Separate summaries will be produced for the following categories:

- Serious adverse events
- Adverse events that are possibly or probably related to vaccine
- Adverse events of special interest
- New onset of chronic disease
- Adverse events leading to withdrawal
- Adverse events resulting in death

Data listings of all adverse events will be provided by subject. In addition, adverse events in the categories above will be provided as listed data.

For handling of missing data, the entire study period will be divided into disjoint intervals based upon the time and event schedule in the protocol:

Solicited AEs: 30 min, 6h-Day 3, Day 4-Day 7, and one overall interval: 6h-Day 7.

Unsolicited AEs: [Day 1-22], [Day 23-181], and [Day 1-181].

No imputation of missing solicited or unsolicited AEs will be used. The percentage of subjects with missing solicited AE assessments (eg, missing Diary Card) and missing Safety Phone Call or safety assessment will be reported for each time period.

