11.2.5.6 Concomitant Medication

The numbers and percentages of subjects reporting concomitant medications will be tabulated overall and by vaccine group and study period (Treatment by Day 1-21, Day 22-Day 181). Medications (generic drug name) will be coded using the World Health Organization (WHO) Drug dictionary (see section 8.7 for definition).

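### Read literally, the unsolicited-AE intervals stop at onset Day 181 while the final call can fall as late as Day 195, so a few collected SAEs, AESIs, NOCDs and other key events could miss their category tables

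*SAP*

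**What the plan says.** SAP 11.2.5.4 sets three onset periods: "Onset between Day 1 and Day 22", "Onset between Day 23 and Day 181", and an overall Day 1 to Day 181 period. The allocation rule is explicit: "The selection of unsolicited AEs and the assignment to time intervals will be done by day of onset". Protocol 8.4.4.3 gives the same periods ("Unsolicited AEs: [Day 1-22], [Day 23-181], and [Day 1-181"]), and so does SAP 8.2.1. Both of those sections present the intervals as a division of the entire study period.

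Collection is tied to visits and calls, which have windows:

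- **Day 22 visit.** Protocol 3.1: "Subjects will return to the clinic on Day 22 (window, Day 19 to Day 25"). All unsolicited AEs are collected up to this visit. Protocol 7.1.2 then narrows the scope: "After the day 22 visit, only unsolicited adverse events, and medication used to treat them, which meet criteria for the following will be collected". The four types that remain are SAEs, AESIs, NOCDs and events leading to discontinuation.
- **Final call.** Protocol 3.1, Follow-up Period: "A scripted safety telephone call will be made by qualified site staff on Day 181 (window: Day 167 to Day 195"). Under Protocol 5.5 this call asks about hospital and emergency care since the last contact, and completing the termination page ends participation.

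For concomitant medications, SAP 11.2.5.6 uses a different split, "Treatment by Day 1-21, Day 22-Day 181", although Protocol 6.5 records all medications from Day 1 to Day 22.

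**The concern.** The intervals have fixed numeric ends, while collection ends on a date that varies by subject. Where the call comes after Day 181, an SAE with onset on, say, Day 188 is asked about, recorded and reportable under Protocol 7.1.6, yet it meets none of the three onset definitions, including the overall one. The tables by category in SAP 11.2.5.4 (SAEs, fatal AEs, AESIs, NOCDs, withdrawal AEs) are presented by those periods, so the event would be absent from them. These tables carry the secondary safety objective in a study meant to support licensure in adults aged 65 and above.

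The Day 22 boundary raises a lesser issue. An ordinary AE on Days 23-25, reported at a late Day 22 visit, counts as any unsolicited AE in the Day 23-181 period, when other subjects contribute only the four restricted event types. That row, and the same row for Days 1-181, then mixes two levels of ascertainment.

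**Working it through.** **1. Reproduce the windows.** Protocol Table 1 and SAP Table 3-1 give -14 to +14 days for the final call and -3 to +3 days for the Day 22 visit.

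- 181 - 14 = 167 and 181 + 14 = 195, which matches the Day 167 to Day 195 in the text.
- 22 - 3 = 19 and 22 + 3 = 25, which matches Day 19 to Day 25.

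**2. Check each possible onset day from 1 to 195 against the three intervals.**

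| Onset day | Days 1-22 | Days 23-181 | Days 1-181 |
|---|---|---|---|
| 1-22 | yes | no | yes |
| 23-25 | no | yes | yes |
| 26-181 | no | yes | yes |
| 182-195 | no | no | no |

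The uncovered stretch is 195 - 181 = 14 days. Days 23-25 are covered, so no collected event is lost at the Day 22 boundary.

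**3. Illustrate the size.** The documents give neither the distribution of call dates nor an SAE rate, so both are assumed here. SAEs are also assumed to arise evenly over time, one per affected subject.

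- Calls spread evenly over the 29 days 167-195: share after Day 181 = 14/29 = 48%.
- Mean time observed beyond Day 181 = (1 + 2 + ... + 14)/29 = 105/29 = 3.62 days per subject, and 3.62/181 = 2.0% of follow-up.
- Expected SAEs outside every interval = 1778 × rate × mean over-run / 181, where 1778 is planned enrolment.

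| Call dates | Mean over-run (days) | SAE rate 3% | 5% | 8% |
|---|---|---|---|---|
| All by Day 181 | 0 | 0 | 0 | 0 |
| Uniform, Days 167-195 | 3.62 | 1.1 | 1.8 | 2.8 |
| All on Day 195 (extreme) | 14 | 4.1 | 6.9 | 11.0 |

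The 1778 is taken before the 10% drop-out allowance. The number of subjects reaching a final call would be lower, and the counts shrink in proportion.

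**4. Where an event with onset on Days 182-195 would still be seen.**

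- Protocol 8.4.4.3 plans listings of all AEs by subject.
- SAP 11.2.5.5 plans a combined solicited and unsolicited summary with no onset limit, but without a split by seriousness.
- Protocol 3.8 counts death as a reason for premature withdrawal, and SAP 9.1 tabulates those reasons by group.

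**The case against.** The strongest reply is that Day 22 and Day 181 are visit labels. Footnote 10 of the Time and Events Table explains Day 22 as up to and including the day of that blood sample. The duration formula in SAP 8.8 attaches Day 181 to the last visit date. Protocol 3.2 and 3.9 speak of the Day 181 call as the last contact. Protocol 8.4.4.3 says the intervals follow the time and event schedule. On that reading nothing falls outside, and the onset rule only separates onset from persistence.

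This has real support, but neither document applies the convention to these intervals. Their bounds are bare day numbers attached to an onset rule, and a programmer would code them as such.

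The opposite reply is that calendar Day 181 is intended, because Protocol 8.1.3, SAP 2.2.4 and SAP 11.2.5.4 describe these events as collected up to Day 181. That gives every subject the same nominal period. But it then conflicts with a final call that reaches back to the last contact without a cut at Day 181, and with the aim of dividing the entire study period. On either reading the passages need to be reconciled.

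Three further objections stand. The events do not disappear from reporting (step 4). The counts depend on assumptions. The study is double-blind and the windows are the same in all arms, so no distortion between arms is expected.

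**Conclusion.** The gap is real on the text, but small. Followed literally, the plan omits SAEs, AESIs, NOCDs, withdrawal AEs and fatal AEs with onset on Days 182-195 from their interval-based tables. The likely number is about 1 to 3 SAEs under uniform call dates and a 3-8% SAE rate, and zero if all calls fall by Day 181. The 4 to 11 obtained with every call on Day 195 is an extreme bound.

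A reader might infer more than the documents support:

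- **That such events would appear only in listings.** They would not: the combined AE summary includes them, and disposition includes deaths.
- **That any death after Day 181 drops out.** Fatal AEs are placed by onset, so a death on Day 188 from an AE that began by Day 181 is still counted.
- **That collected events are lost at Day 22.** None are. The issue there is mixed ascertainment in the later and overall rows for any unsolicited AE.

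The Day 21/22 medication split is a plain inconsistency with the collection period. It loses nothing, because its periods are contiguous and an overall tabulation is planned. The co-primary analyses are unaffected.

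**What to change.** Before unblinding, amend SAP 11.2.5.4 and 8.2.1, and align Protocol 8.4.4.3:

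- First interval: Day 1 through the actual date of the Day 22 visit.
- Later interval: the day after that visit through the study termination date.
- Overall interval: Day 1 through the study termination date.
- Show any unsolicited AE for the first interval only. For the later and overall intervals, show SAEs, AESIs, NOCDs, withdrawal AEs and fatal AEs.
- In SAP 11.2.5.6, replace the Day 21/22 split with the same boundary.

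The SAP should also state which date applies when a subject has no Day 22 visit.

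The cost is SAP wording and table programming. The one downside is that interval lengths will differ by a few days between subjects. The change does not recover ordinary AEs that go uncollected up to Day 22 after an early visit on Days 19-21. That is a consequence of the visit window, and redefining the intervals cannot remedy it.

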11.2.5.5 Combined Solicited and Unsolicited Adverse Events

A summary of the number of subjects with all combined solicited (regardless of their duration) and unsolicited AEs will be provided, regardless of their duration and recurrence. A further differentiation of combined AEs according to seriousness, severity, or relationship will not be performed. For clintrial.gov and EudraCT posting purposes, a summary of combined solicited and unsolicited non-serious AEs will be produced by System Organ Class and according to occurrence of each event.

11.2.5.6 Concomitant Medication

The numbers and percentages of subjects reporting concomitant medications will be tabulated overall and by vaccine group and study period (Treatment by Day 1-21, Day 22-Day 181). Medications (generic drug name) will be coded using the World Health Organization (WHO) Drug dictionary (see section 8.7 for definition).

11.3 Analysis of Exploratory Objectives

The exploratory objectives are:

1. Additional optional objectives include characterization of the immunogenicity of aQIV using other immunological assays (e.g., virus neutralization [MN] or anti-neuraminidase antibody assays may be performed)
2. To explore the association between immune response after administration of aQIV or the aTIV-1, containing the same virus strains as the US-licensed adjuvanted trivalent influenza vaccine, or the aTIV-2 containing the alternate B strain by baseline characteristics.

Exploratory immunogenicity objective 1

Exploratory objectives related to the MN-assay, immune response to heterologous influenza strains, or different antigens will be evaluated using similar methods for log normal, binomial data, and GMT and SCR as described in the statistical method for primary and secondary immunogenicity analysis.

Exploratory immunogenicity objective 2

- GMTs: Geometric mean of HI titers prevaccination (Day 1) and at Study Exit Visit
- Percentage of subjects with four-fold rise

Analyses of the exploratory immunogenicity endpoints will be performed with adjustment for covariates including prevaccination titer, vaccination history, age and gender to evaluate the contribution of these factors to variations in the immune response. The covariate adjustment will be performed with all of the specified covariates in the general linear model.

The full model specification for the GMT titers (for each strain) will be:

Log-transformed Post-Vaccination HI Titer = Vaccine + Age Strata + Gender + Vaccination History + Log-transformed Prevaccination HI Titer.

The full model specification for the SCR rates will be:

SCR = Vaccine + Age Strata + Gender + Vaccination History + Log-transformed Pre-vaccination HI titer

SCRs will be analyzed using a logistic regression model, and GMT titers will be log transformed (base 10) and analyzed with a general linear model. Pre-vaccination titers will be log transformed (base 10) and entered as a continuous covariate. Vaccination history will be a categorical variable indicating whether or not an individual received an influenza vaccination in the previous year. If the proportion vaccinated in the previous year is close to 100% then this covariate may be omitted to avoid creating an unstable model. Age will be entered according to the predefined strata ($\geq 65-74$, $\geq 75-84$, and ≥ 85 years). For the logistic regressions, the odds ratios will be presented with 95% CIs for each effect in the model. For the GLM least square mean estimates for the GMT ratio will be presented with 95% confidence limits for each effect in the model.

11.4 Interim Analysis

No interim analysis is planned for this study.

12. EFFICACY ANALYSIS

NA.

13. DATA MONITORING COMMITTEES

An independent Data Monitoring Committee (DMC) will not be utilized for the study.

14. CHANGES TO PLANNED ANALYSES FROM PROTOCOL

All FAS in the protocol (dated 17MAY2017) corresponds to FAS immunogenicity in this document. The protocol is to be updated to match the language in this document.

